12 REGULATORY ASPECTS AND PROTECTION OF SUBJECTS

The study will be conducted in accordance with French regulations applicable to the "études interventionnelles à risques minimes" at the date of approval of the Clinical Investigational Plan by the sponsor (Loi Jardé). The study will be submitted to a Committee for the Protection of Persons (CPP) with a notification to the National Agency for the Safety of Medicines and Health Products (ANSM) required by the texts.

The study will be conducted by Lohmann & Rauscher/RCTs in compliance with the regulations, the Helsinki Declaration and the applicable Good Epidemiological Practices including the recommendations of Ethics and Good Practices in Epidemiology (ADELF Version France - 2007) and the Guidelines for Good Pharmacology Practices (ISPE - 2008).

Lohmann & Rauscher/RCTs are committed to putting in place appropriate procedures to ensure the protection and well-being of subjects who will participate in this study. By agreeing to participate in the study, the study nurse agrees to abide by applicable regulations, protocol, applicable good practices and procedures for conducting the study.

13 BENEFITS AND RISKS

The study does not require any additional tests, consultations or treatments compared to the care patients would normally receive. Apart from the choice of the dressing, which will be made at random, the study will not change in any way the treatment patients receive from the nurse. There are no constraints for patients and no specific risks related to their participation. Patients' participation in the study will not prevent healthcare professionals from using other treatments or ordering further investigations as needed for patients' care. The main constraint related to the patients' participation will be to follow carefully the advice of the healthcare professionals who provide care for their wound. If, during the study, patients do not tolerate the dressing or if, based on the way their wound progresses, the dressing is not right for them, the healthcare professional will decide what treatment would be most suitable for the patient.

Version 2.0 – March 29, 2019

The study nurses participating in this study are remunerated and the study Clinical Investigational Plan (or summary) and the financial agreements of the participating study nurses will be submitted to the National Council of the Study Nurses (CNOI, Article L.4113-6 of the Code of Public Health) by RCTs, on behalf of Lohmann & Rauscher.

Each participating study nurse will receive a copy of his/her contract with the opinion of the CNOI and any correspondence between RCTs and the CNOI or, if applicable, a letter from RCTs stating that the financial contract has been submitted to the CNOI and the period of 2 months having elapsed, the opinion of the CNOI shall be deemed to be favourable.

Each participating study nurse will have to send a copy of the CNOI's opinion or the letter of RCTs to its Departmental Council of the Order accompanied by a copy of its financial agreement (Articles L.4113-9, L.4113-10 and L.4163-10 of the Code of Public Health).

15 SUBMISSION TO THE COMMISSION NATIONALE DE L'INFORMATIQUE ET DES LIBERTES (CNIL)

Since this study requires collecting and processing personal data with the purpose of research in the field of health, it depends on chapter IX of the Modified Data Protection Act of January 6th, 1978.

As a "études interventionelles à risques minimes" organized and practised on/with human beings with the purpose of developing biological, medical or health knowledge in which all the acts are practised and products are used in a usual way, without any additional or unusual procedure of diagnosis, treatment or surveillance possibly related to databases and\or biological collections of samples which are pre-existing, legally established and have been the object of the necessary formalities of declaration and\or of authorization with competent authorities", it enters the perimeter of the Reference Methodology 001 (MR001). The data collected within the framework of the study are also in accordance with the MR001 and strictly limited to the necessary and relevant data with regard to the objectives of the research.

The necessity to collect indirectly personal data (identification of the subject by a number of inclusion with the following format: XX-YY, where XX is the site number and YY the number of patient included in the site) is justified by the necessity of being able to make requests for further information with the participating study nurses in the case of questionnaires, guarantee the quality of the data, be able to control in case of dispute during the computerization of the data and allow the study nurses to identify the subject that must be the object of a delayed collection of data.

The study nurse will have to fill in and keep a cross-reference table allowing them to return to the patient file according to its order number of inclusion in the study to be able to answer these requests.

Under the modified "Computing and Liberties" law of January 6th, 1978, the patient will be informed of his right of access, opposition and rectification regarding the data recorded on the occasion of this study, this right being applicable at any time with the study nurse.

Personal data relative to the participating study nurses will be declared and the study nurses will be informed within the framework of their financial agreement of their right of access, opposition and rectification of these information.

Version 2.0 – March 29, 2019

16 SCHEDULE

Study start: Enrolment of the first patient, defined as date of signing of the study nurse form Study end: analysis and assessment of all collected clinical data is finalised, defined as time of finalisation of the study report

The expected study duration is 24 months.

The expected study duration per patient is 3 weeks.

18 APPENDICES

18.1 Photographic pictures

The photographic images are to be produced using a digital camera with a resolution of at least 3 million pixels and under the following standard conditions:

At visit V1, two photographs are to be taken: one after cleaning the wound and one after placement the product to the wound (before placement of a secondary dressing). At visit V2 three photographs are to be taken: one prior to removing the dressing (but after removing the secondary dressing, if any), one after cleaning the wound and one with the product on the wound (after placement the new product to the wound but before placement of the secondary dressing). At visit V3 (or Early termination visit, if performed instead) two photographs are to be taken: one prior to removing the dressing (but after removing the secondary dressing, if any) and one after cleaning the wound.

Instruction for the wound photography (without dressing):

- 1. Place the patient in a position that will ensure the best possible visibility of the wound.
- 2. Rinse the wound with a 0.9% saline solution and dry it with a sterile gauze pad.
- 3. Place the millimetre ruler above or below the wound. The patient's ID number and the date of the evaluation should be clearly visible on the ruler.
- 4. Hold the digital camera in a position perpendicular to the surface of the wound. Position the camera in such a way that the wound occupies as much of the visual field of the camera as possible. Ensure that the millimetre ruler provided by the Sponsor is in the visual field.
 - Place the centre of the wound in the centre of the visual field.
- 5. Photograph the wound with the automatic settings of the camera and control the following features:
 - neutral background (do not use white fabric)
 - absence of external stray lighting
 - absence of fluid on the wound
 - absence of any objects in the visual field of the camera

18.2 Protocol for Removal of the Primary Dressing

Wound care is to comply with the reference text "Individualised dressing of clean wounds, whether sutured or not, septic wounds" issued by the CCLIN* Sud-Ouest (1997 revised).

The primary dressing is to be removed in accordance with the following instructions:

Before proceeding to remove the dressing, it is preferable to warn the patient that the dressing will be removed.

Use a sentence such as "Now we're going to take care of your wound. Don't hesitate to stop me if anything bothers you while I'm doing that".

Do not use sentences like "This might hurt a little" or "I'm going to do my best to try not to hurt you".

After removing the elastic compression strapping or other orthotics, if any, remove the secondary dressing.

Visually inspect the primary dressing.

If the dressing appears to be dry and is obviously adherent to the wound, it should be soaked with sterile saline solution.

Remove the dressing using sterile forceps or a non-sterile disposable glove.

Delicately peel back one of the edges and then gently remove the dressing all in one piece by pulling in the direction the hair grows. If you meet resistance, soak the dressing with saline solution.

Inspect the wound bed for bleeding, if any, and grade any bleeding you detect.

Assess the pain induced by removal using the visual analogue scale (VAS). Do not communicate the result to the patient.

^{*} CCLIN is the Centre for coordination of the fight against hospital-acquired and care-related infections

18.3 Assessment of Pain using Visual Analogue Scale

In all cases:

[figure not shown]
- Check the patient's visual acuity (provide correction, if needed)
- Check that the patient understands how the scale is used

18.3.1 Visual Analogue Scale

The VAS is used to grade the patient's pain and pain relief. It is a scale from 0 to 100 mm whitout any millimetter marks. The ends correspond to "0 = no pain" and "100mm = unbearable pain".

This specific ruler will be provided to the investigator in order to measure the VAS score. The subject will mark on the ruler the point that he/she feels represent his/her perception of his/her current pain. The VAS score will be directly measured by the investigator. The VAS score will be filled in the CRF.

Visual Analog Scale

When presented to the patient, the scale should be in the **horizontal position**. The patient should be asked to rate his/her pain in relation to a prior usual type of pain, for example, "When you have a headache, where would you say you are on the scale? And what is the pain like now? Stronger or not as strong?").

The **result in millimetres** is to be noted on the CRF form. It should not be **communicated to the patient**.

The method requires good motor coordination on the part of the patient, and it has other limitations, e.g. patients with limited capacity for abstract thought, those with poor eyesight and the elderly.

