7.2.2.2 Intermediate visit (V2, D3±2)

The intermediate visit must be planned three days after the first investigational product application. If appropriate, a window of two days before or after this expected visit is allowed to make sure that the patient will have the first dressing change as early as necessary according to their condition (i.e. already on the next day after V1).

Adverse events (AEs) / Serious adverse events (SAEs) / Adverse device effects (ADEs) and Device deficiencies (DDs) occurring since the previous visit will be collected by the investigator. Any changes to the concomitant therapy will also be collected. The investigator will also ensure that the subject continue the investigation.

The presence of complete healing status (100% of epithelialization, first epithelia layer) of the wound) will be assessed.

NB! In case of complete epithelialization all procedures, required for Visit 3 should be

performed, data is to be recorded in the CRF section Visit 3. Visit 2 should be marked as "Not performed due to early epithelialization" in the CRF.

Depending on the subject condition, analgesics may be concomitantly prescribed by the investigator. In this case, details on the type of prescribed treatments belonging to analgesic therapeutic class as well as hour of intake before removal (within 2 hours notably) will be recorded in the CRF.

A photograph of the wound with the investigational product in place will be taken before product removal (but after secondary dressing removal, if there was any), according to the photography guidelines (see Appendix 17.1).

The investigator will remove the investigational product by following the standardized removal procedure (see Appendix 17.2). Data about dressing soak will be collected in the CRF.

Pain at the first dressing removal will be assessed by using the visual analogue scale (VAS). The investigator will ask the subject to assess his/her pain level at the dressing removal. The subject will be asked to rate the pain he/she felt at the moment of dressing change using the VAS tool.

After product removal, a photograph of the wound will be taken according to the photography guidelines.

The investigator will assess the wound and surrounding skin condition:

- Wound size estimation
- Assessment of the wound bed (bleeding, maceration, inflammation, infection, ratio necrotic/ fibrinous/ granulation/ epithelisation tissue, and tissue in-growth in the dressing holes)

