7.8.2 Efficacy Measurements and Variables

7.8.2.1 Main Objective

Variable

The main criterion corresponds to the percentage of non-painful dressing removals defined as the percentage of dressing removals associated with a value < 30 mm on a VAS assessing pain scale (0 to 100 millimeters) evaluated at the first dressing removal (V2, D3±2).

This 30 mm threshold is recognized to differentiate a weak pain (score <30 mm) from a moderate (score ≥30 mm) to severe (score >50 mm) one [9-12].

Measurement

Subjects will be asked by investigators to rate their pain intensity perceived at the first dressing removal (V2, D3±2). Pain assessment will be performed using a Visual Analog Scale (VAS). The VAS is a 100 mm straight line ranging from 0 to 100, on which the subject will indicate his/her pain. Subjects will beforehand be informed that the beginning of the scale refers to "no pain" (0) and the end to the most severe intensity of pain they can have (100). Painless dressing change is defined as pain < 30 mm on the VAS. The results obtained during the first dressing removal visit (V2, D3±2) will be filled in by the investigator in the CRF.

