18.3.2 Evaluation of Pain on Removal of Dressing

The patient is placed in the most comfortable situation possible taking into account the constraints related to providing wound care and to the location of the wound.

If prior care was painful or if you are planning to perform debridement of the wound, it is possible to prescribe oral analgaesia. Note your prescription on the follow-up form.

Remove the secondary dressing. The primary dressing is then removed in accordance with the standardised protocol.

Immediately after removing the dressing and before performing any local wound care, assess the patient's pain using the VAS. If the VAS is not suitable in view of the patient's status, use the numerical scale.

Note the result on the CRF form, but do not communicate it to the patient.

Then, continue your assessment of bleeding, if any, and proceed with wound care.

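### The instructions for the primary V2 pain score contradict each other: Appendix 18.3.1 asks for current pain, while the endpoint is pain at dressing removal

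*Protocol*

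**What the plan says.** **Which pain is scored.** Section 7.2.2.2 has the patient "rate the pain he/she felt at the moment of dressing change". Table 1 (7.2.1) and the list of major deviations (10.2) label the V2 score as pain during removal. Section 7.8.2.1 asks for the intensity perceived at the first removal, and 18.2 for the pain that removal induced.

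Appendix 18.3.1 differs: "The subject will mark on the ruler the point that he/she feels represent his/her perception of his/her current pain". It adds "The patient should be asked to rate his/her pain in relation to a prior usual type of pain", gives a headache as the example, and offers the prompt "And what is the pain like now? Stronger or not as strong". Section 7.2.2.1 uses the same current-pain sentence for the V1 score, which is taken after application.

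**When it is scored.** Appendix 18.3.2 places the VAS immediately after the dressing is off and before local care. It refers only to the patient's pain, without tying it to the removal. It continues: "Then, continue your assessment of bleeding, if any, and proceed with wound care". Appendix 18.2 has the reverse order. Its step before the VAS is "Inspect the wound bed for bleeding, if any, and grade any bleeding you detect".

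**The 100 mm end.** Section 7.8.2.1 describes "the end to the most severe intensity of pain they can have (100"; 18.3.1 describes pain that is unbearable.

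The supplied SAP is written for another product (Suprasorb C) and does not settle any of this.

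**The concern.** This score alone decides the trial. Removal pain may be brief, so pain felt at removal and pain present once the dressing is off can differ. A nurse who follows 18.3.1 as written records the second; one who follows 7.2.2.2 or 18.2 records the first. About 100 nurses are to enrol 168 patients (168/100 = 1.7 each), so a nurse has little chance to settle into a common practice and depends on the written instruction. A score in the CRF would not show which question was asked.

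The direction matters in a non-inferiority trial. If painful removals are scored below 30 mm in both arms because the pain has passed, a true difference shrinks and non-inferiority becomes easier to show. Analysing both the PP and mITT sets does not remove this, since both use the same score.

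**Working it through.** **1. The texts side by side (V2 score)**

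| Protocol section | Pain to be rated | VAS relative to bleeding |
|---|---|---|
| 7.2.1, 10.2 | during removal | not stated |
| 7.2.2.2 | felt at the moment of change | not stated |
| 7.8.2.1 | perceived at first removal | not stated |
| 18.2 | induced by removal | after grading |
| 18.3.1 | current, now | not stated |
| 18.3.2 | the patient's pain, unspecified | before |

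Five places name removal pain, one names current pain, and one leaves it open. The two orders in 18.2 and 18.3.2 cannot both be followed.

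**2. The plan's sample size, for reference.** Inputs from 7.9.2: 95% success in both arms, margin 10 points, one-sided 2.5%, power 80%.

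n = (1.960 + 0.842)² × 2 × 0.95 × 0.05 / 0.10² = 74.6, so 75 per group; 75/0.9 = 83.3, so 84. The plan's figures reproduce, and this point does not change them.

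**3. What fading would do (illustration).** The documents give no share of painful removals that would fade below 30 mm. Call it f, assume it is equal in both arms, and take true success of 95% (UrgoTul) and 85% (Lomatuell Pro), exactly at the margin. Observed success is 1 − 0.05(1 − f) and 1 − 0.15(1 − f), so the observed difference is −10(1 − f) points.

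The table gives the chance of wrongly declaring non-inferiority by exact binomial enumeration, with 75 scored patients per arm and a lower one-sided 97.5% limit above −10 points. The protocol names no interval method, so Newcombe is shown with Wald in brackets. The last two columns apply the rule in 7.9.1.2: PP and mITT must both pass, and missing scores count as failures. There the PP set is 75 per arm and the mITT set is 75 plus the missing, i.e. 79 or 84.

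| f | Observed success | Difference | One set of 75 | Both sets, 4 missing per arm | Both sets, 9 missing per arm |
|---|---|---|---|---|---|
| 0 | 95% / 85% | −10 | 2.6% (3.7%) | 1.2% (1.5%) | 0.6% (0.6%) |
| 25% | 96.25% / 88.75% | −7.5 | 7.9% (12.3%) | 3.6% (4.8%) | 1.5% (1.9%) |
| 50% | 97.5% / 92.5% | −5 | 22.8% (36.4%) | 10% (15%) | 4.3% (5.2%) |

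Nine missing per arm is the case in which all the planned attrition (84 − 75) is missing V2 pain. If no score were missing and no one else were excluded, the two sets would coincide and the joint rule would give no reduction.

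**4. The other direction.** Current pain also includes background wound pain, which can lift a score to 30 mm or more. If 5% of successes in each arm were lost in this way, with truly equal arms at 95%, observed success would be 0.95 × 0.95 = 90.25%. Power in a single set of 75 would then fall from 72% to 52% (Newcombe).

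**The case against.** The strongest reply is that the intended target is clear. Appendix 18.3.1 reads as general text on the tool, which covers pain relief as well as pain, and its current-pain sentence recurs at V1. The procedure that nurses must follow at V2 is 18.2, which ends by asking for the pain induced by removal, and 18.3.2 has a heading about pain on removal. Scoring is to be immediate, and even under 18.2 only the bleeding check comes between. This stands in part. It rules out reading the protocol as a uniform instruction to score the wrong pain, and it shows that 18.2 agrees with 7.2.2.2 on the target, differing from 18.3.2 only on order. It does not remove the contradiction, because 18.3.1 is the page that supplies the words put to the patient.

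Three stronger inferences are tempting, and the documents do not support them:

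- **That a rating against a headache is off the 0 to 100 mm scale and voids the 30 mm cut-off.** The headache is only an example, and the result is still a millimetre mark between fixed ends. Both wordings of the upper anchor describe extreme pain. The scale figure is not in the text and the CRF was not supplied, so the wording on either may be clearer.
- **That the endpoint is worst or peak pain.** No section says so.
- **That the trial is biased towards non-inferiority by a known amount.** The fading share is assumed, fading may differ between arms, and background pain can work the other way.

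**Conclusion.** The contradiction is established from the text: the sections disagree on which pain is scored, on whether bleeding is graded first, and on the wording of the upper anchor. Some V2 scores may therefore measure residual or background pain in place of removal pain, and the analysis could not tell which.

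Neither the size nor the net direction can be derived from the documents. The single-set figures of 7.9% and 22.8% assume fading shares of 25% and 50%, equal fading in both arms and a true difference at the margin. Under the joint PP and mITT rule they fall to 1.5% to 3.6% and 4.3% to 10%, with 9 or 4 missing scores per arm. They show how the mechanism would work; they are not an estimate for this trial.

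This should be fixed, because it concerns the only primary measurement and the remedy is cheap. It is not evidence that the trial would reach a wrong conclusion.

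**What to change.** For the V2 score:

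- In 18.3.1, replace the references to current pain and to pain now, and in 18.3.2 the unspecified reference to the patient's pain, with the target already set in 7.2.2.2 and 18.2: the pain felt during removal of the primary dressing.
- In both 18.2 and 18.3.2, take the score immediately after removal and before bleeding is graded.
- Use the comparison with a familiar pain such as a headache only to check that the patient understands the scale.
- Use one wording of the 100 mm anchor in 7.8.2.1, 18.3.1, the ruler and the CRF.

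The cost is a wording change to the protocol, its appendices and any ruler or CRF instruction, with a note to the nurses. It needs no extra visit, staff or data, and the sample size stays at 84 per group.

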18.3.2 Evaluation of Pain on Removal of Dressing

The patient is placed in the most comfortable situation possible taking into account the constraints related to providing wound care and to the location of the wound.

If prior care was painful or if you are planning to perform debridement of the wound, it is possible to prescribe oral analgaesia. Note your prescription on the follow-up form.

Remove the secondary dressing. The primary dressing is then removed in accordance with the standardised protocol.

Immediately after removing the dressing and before performing any local wound care, assess the patient's pain using the VAS. If the VAS is not suitable in view of the patient's status, use the numerical scale.

Note the result on the CRF form, but do not communicate it to the patient.

Then, continue your assessment of bleeding, if any, and proceed with wound care.
